### *Trial intervention*

The trial intervention includes a new experimental educational approach; in vitro simulation-based TUS training. The TUS module for the US Mentor Simulator is made in collaboration with 3D Systems (3D Systems Healthcare, Littleton, USA, formerly known as Simbionix). A TUS expert developed nine cases, and the cases cover the most common causes of respiratory failure, dyspnoea and cough. The content and curriculum of the educational programme are based on the guidelines and recommendations from the Royal College of Radiologists [3], European Federation of Societies for Ultrasound in Medicine and Biology [4], International evidence-based recommendations by Volpicelli et al. [1], and Lung ultrasound in the critically ill by Lichtenstein et al [5].

This simulation model will serve as first intervention arm, and after the introduction to the ultrasound machine, the group randomized for simulation training is allowed to practice for 2.5 hours before assessment.

The second intervention arm in the trial is a commonly used hands-on training method; examination of healthy volunteers (figurants), in this case medical students who signed up for the job, and who is a part of the research group. Trainees are as well allowed to train for up to 2.5 hours, but the medical students are not allowed to help or guide the trainee during the examinations.

Last group will not receive any hands-on training other than the general information, and will serve as controls. Figure 1 present a flowchart of the trial.

When trainees have finished the hands-on training, they will continue to assessment of competencies, done by an instructor blinded to the intervention. The medical student will inform the instructor, and the assessment will take place in the emergency department examining real patients suspected to have thoracic pathology/pathologies. As assessment tool the LUS-OSAUS score sheet is used [6]. The assessment will be repeated twice.

### *Blinding*

It is not possible to blind the participants to the educational intervention, but the instructor assessing the participants is blinded to the intervention. The data-managers providing the statistical analysis are going to be blinded when performing the analyses and when drawing conclusions of the results.

### *Measurements and assessment of outcomes*

Appendix 1 covers the present codebook (version 1.0, July 2018) of variables, including type of variables, legal values and labels. Table 1 provides an overview of the outcomes, and statistical analyses, and Table 2 a timeline for obtaining data and registration in the database.

### *Outcomes*

The primary outcome is difference in LUS-OSAUS score between the three groups [6]. The LUS-OSAUS score is calculated as the sum of all 17 items in the tool (min. 17, max. 85 point), evaluated by instructor and first author, PP. The participant is evaluated two consecutive times.

The LUS-OSAUS tool is, to our knowledge, the first assessment tool with established evidence of validity. The publication shows that LUS-OSAUS can differentiate between different levels of competencies.

Secondary outcome is difference in number of scans performed from baseline to follow-up (4 months) between the two intervention arms.

### *Sample size*

Significance 5%, Power 90%, mean difference wanted between the two interventional groups is 8.5 point. Standard Deviation 8.67. Sample size per group is 22 (total; 66 participants).

### *Statistical analyses*

Data will be accessed using OPEN analyse, and analysed using STATA and SPSS. OPEN Analyse is an analyse environment that complies with the current regulations on data privacy. OPEN Analyse acts as terminal server solution from the researcher's private PC with logging if files, but data are stored and processed on a server at the Regional IT.

A two-sided significance level of 0.05 will be used. Statistical methods for the primary and secondary outcomes are presented in Table 1, and include Post Hoc ANOVA with Bonferroni correction, hands-on training facility as independent variable (SIM, FIG, controls), and LUS-OSAUS scores as dependent variable.

All data will be analysed as intention to treat, therefore missing data will be handled by multiple imputation technique, even though missing data are expected to be minimal because instructors are registering a great amount of the data to the database.

### *Ethical considerations*

Participants are physicians, and even though patients are used for assessment, no patient data are going to be used. Neither participants nor instructor will look in the electronic patient database, or at previous radiological examinations. The patient will be given oral information about the trial including aim, running and assessment of participants, and that ultrasound is a non-invasive and radiation-free radiological examination with no risk of complications or side effects. Subsequent, orally informed consent will be given from the patient. If the ultrasound examination provides further information to the patient inquiry, which is suspected as new information, the physician in charge of the patient will be informed orally.

The trial complies with the Declaration of Helsinki on biomedical research and with the act on processing personal data. The Regional Committees on Health Research Ethics for Southern Denmark has been given the project description and protocol, and found that in accordance to Danish regulations, ethical approval is not required for carrying out the trial (S-20172000-44).

The trial is notified to the Danish Data Protection Agency under the in Region of Southern Denmark, and, as prescribed, a data management contract is going to be signed with authors and supervisors outside the region. The trial is going to be registered at [www.clinicaltrials.gov](http://www.clinicaltrials.gov) when the account access is available.

The educational programme is planned to include two parts, the web-based theoretical session which participants can access at all time, and the hands-on session planned to take place during normally working hours. Participants are not going to receive salary or compensation for the participation in the educational programme. The educational programme is offered by the Simulations Centres in the Regions, and is therefore free of charge for physicians employed at the public hospitals. Participants can at any time withdraw from the trial.

Participants are assured written and orally, that personal data (including questionnaire and assessment scores) are anonymized, and will remain this way during data management, storage, analyses and reporting or publication.

### *Discussion*

The presented trial is set to investigate whether a TUS simulator as hands-on training facility, can provide a higher level of competencies after 2.5 hour training, than training on healthy figurants, which is a commonly used model today [7-9].

Simulation-based medical education (SBME) has several advantages, and is a complex educational intervention that enables both immersive and experimental learning, and makes it possible to acquire and maintain skills in a calm and safe environment without putting patients at risk if a wrong decision or interpretation is made [10]. The use of this approach has increased within the last decade, and in various specialities using technical procedures [11-13].

Furthermore, all pathologies considered mandatory to the content or course are possible to explore, and a trainee is able to practice a particular case or high-risk cases, over and over again, if doubt arises or if the trainee does not provide a satisfying result. Seen in a research perspective, SBME makes it possible to compare results of different trainees for research purpose, because of a standardized set-up. On the other hand, disadvantages in simulation training appear; e.g. if the fidelity drops for a short moment, the trainee may use a lot of effort to move back into the simulation setting, the technical models require updates, maintenance, and an instructor is often necessary in the beginning for introduction, and for emphasizing trainee reflection and peer review elements [10]. Last, but not least simulation training cannot replace traditional apprenticeship or stand alone, but must be seen as and add-on approach prior to supervised training in a clinical setting [10,14].

Today in TUS, it is often a fixed number of examinations on patients that determines whether a physician can do a sufficient ultrasound examination sufficiently [3,4,15]. Otherwise a supervisor, subjectively, accepts and approves a trainee's skills, but none of those methods ensure the professional level of competencies, and can be affected by external factors and cause feasibility problems [16]. There will be situations where a patient is seriously ill, and rapid start of treatment is basis for a good outcome. In these situations education is not first priority, and is easily put in line.

Secondly, due to the varying incidence of various pulmonary diseases and pathologies, hands-on training on patients in a clinical setting does not ensure examination of all important sonographic findings [17].

To our knowledge no previous studies have been published, comparing the effects of different hands-on training facilities in TUS. Several studies have shown a positive effect of one particular modality, e.g. laboratory animals [7,18], cadavers [19], phantoms [20], or like in this trial, healthy figurants [21] or simulators [22], but did not compare the effects.

Previous studies that have investigated simulation training in ultrasound of other organ systems than lungs or thorax, or ultrasound guided procedures, have showed large and significant effect when compared to no training [23,24], but in order to provide realistic and transferable comparison the control group should not be no training, but training as is the case today; training on healthy figurants. In order to implement simulation training for gaining TUS competencies, and rethink the educational tasks for physicians, the results for the simulator group are expected to be better than the group of comparison and controls.

### *Limitations*

The study will suffer from a number of limitations. Given the nature of the trial it is not possible to blind the participants, but the instructor assessing the participant is blinded to the intervention. During the analyses and reporting, the allocation will be blinded to the data-managers.

TUS is a quit new modality, and the clinical training during follow-up can be influenced by several factors as; accessibility of an ultrasound machine in the departments of the participants, accessibility of supervision and sparring with other clinicians using lung ultrasound, and attendance on courses teaching TUS from baseline to follow-up. To take this into account, participants will fill out a questionnaire regarding some of the potential co-factors and confounders, to make it possible to stratify for these. Because the trial is randomized we expect these systematic errors and confounders to be randomly and equally allocated in the three groups.

The most optimal primary outcome in educational studies, is a patient-related, clinical outcome, but unfortunately this is not possible.

*Trial status*

Planning of the trial was initiated in March 2017, but validation studies of a written and practical test were needed before initiating this trial. The intervention is scheduled to begin in August 2018 and will continue until April 2019, and follow-up assessments continue until August 2019.

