#### *Prior to intervention*

Prior to the randomization all participants will complete an online educational programme in TUS in order to reach sufficient theoretical knowledge, and must pass a theoretical test and answer a questionnaire regarding previous experience with ultrasound in general and TUS, current position and employment. All included participants will receive a study identification number that makes it possible to pair the results from the questionnaire to the intervention and performances.

All materials needed prior to the theoretical test, including online educational material, log-in to questionnaire and test will be send to the participants by mail as well. The online educational material comprises access to Munksgaards' online portal in basic ultrasound, which includes theoretical sonographic sessions, instruction videos in TUS, practical hands-on demonstrations, ultrasound clips, and vodcasts. The preparation is estimated to 2-3 hours. The theoretical test is administered in Research Electronic Data Capture (REDCap) provided by Odense Patient data Explorative Network (OPEN). Participants will be excluded if they do not complete the test.

When participants have completed the test, they will move on to part two, which is the practical hands-on training. Part two of the trial will take place in one of the simulation centres. All participants will receive an introduction to the ultrasound machine. A medical student working on the project will do the introduction, which comprises following general information about ultrasound but no information about TUS:

- Turn on/off
- Select and change transducer
- Select preset
- Adjust depth, gain and focus
- Store images/clips

Subsequently, the randomization will take place.

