Number of examination performed from baseline among the three groups to follow up (4 months)	Training on simulator gives the trainee a better starting point for doing examinations in the clinical daily work	Participant reported number of examinations performed	Gaussian distribution expected, continuous interval data	Parametric analysis, and ANOVA with Bonferroni correction for multiplicity

Table 2. Timeline of measurements

	Pre study (registration and theoretic session)	Baseline (course day)	4 months
Participant information	X		
Theoretical Test	X		
LUS-OSAUS		XX	
Follow-up questionnaire			X

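### Does the plan need to rule out stratifying the 4-month scan count on course attendance that arises after randomisation?

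*Combined protocol and SAP*

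**What the plan says.** The Limitations section lists three things that may influence clinical training after the course day: access to an ultrasound machine, access to supervision or peer discussion, and "attendance on courses teaching TUS from baseline to follow-up". To deal with them, "participants will fill out a questionnaire regarding some of the potential co-factors and confounders, to make it possible to stratify for these". The next sentence reads: "Because the trial is randomized we expect these systematic errors and confounders to be randomly and equally allocated in the three groups".

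The other relevant statements are these:

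- **Timing.** Under Prior to intervention, randomisation follows the introduction to the machine on the course day. Before that, participants "answer a questionnaire regarding previous experience with ultrasound in general and TUS, current position and employment". Table 2 places a follow-up questionnaire at 4 months.
- **Blinding.** "It is not possible to blind the participants to the educational intervention".
- **Outcome.** "Secondary outcome is difference in number of scans performed from baseline to follow-up (4 months) between the two intervention arms". The Table 1 row for this outcome refers to three groups.
- **Analysis.** The Statistical analyses section refers to Table 1 for the methods of both outcomes. For the scan count, Table 1 gives "Parametric analysis, and ANOVA with Bonferroni correction for multiplicity", with no stratification factor or covariate. The same section states: "All data will be analysed as intention to treat".

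**The concern.** Randomisation balances, in expectation, what exists when it takes place. Course attendance between baseline and 4 months comes later, in people who know which training they received. Untrained controls might look for a course elsewhere, or trainees who enjoyed the session might sign up for more. Attendance would then be partly a result of allocation. It would not be a confounder, and the expectation of equal allocation need not hold for it.

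Comparing arms within attendance strata could then go wrong in two ways. If courses lead to more scanning, stratifying removes the part of the training effect that acts through courses. If motivation drives both attendance and scanning, attenders in one arm are no longer comparable with attenders in the other, and a difference can appear where none exists.

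The Limitations text draws no line between factors fixed before randomisation and those arising later, and does not call a stratified analysis exploratory. A reader could fear that a stratified result would be reported in place of the randomised comparison.

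**Working it through.** **1. Which analysis the plan commits to.** Statistical analyses points to Table 1, and Table 1 gives one method for the scan count: an ANOVA across arms with Bonferroni correction. Under intention to treat, participants are analysed in their allocated arm. The Limitations sentence sits outside the analysis section, says only that stratification becomes possible, covers only some of the factors, and does not say that attendance is one of them. The questionnaire items would be in the Appendix 1 codebook, which is not in the text supplied.

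**2. What cannot be affected.** Table 2 places both LUS-OSAUS assessments on the course day, before any follow-up course. The primary outcome is outside the concern.

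**3. The plan's own figure.** The Sample size section gives 22 per group for the primary outcome, and nothing for the scan count. With a difference of 8.5, SD 8.67, two-sided 5% and 90% power:

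n = 2 × (1.960 + 1.282)² × (8.67/8.5)² = 2 × 10.51 × 1.0404 = 21.9, so 22.

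This reproduces the stated figure. I use 22 per arm below for scale.

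**4. Bias from stratifying when there is no true arm effect.** All inputs here are assumptions. Motivation m is standard normal, and P(attend) = expit(a + b·m), with a solved to give each attendance rate. The scan count is r·m plus error, with total SD 1. The mean count is r·E[m·P(attend)]/p among attenders and r·E[m·(1 − P(attend))]/(1 − p) among non-attenders, where p is the attendance rate. With b = 1 and r = 0.5:

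| Attendance, arm A vs arm B | Non-attenders, A − B | Attenders, A − B | Unstratified |
|---|---|---|---|
| 20% vs 20% | 0 | 0 | 0 |
| 20% vs 30% | 0.040 SD | 0.052 SD | 0 |
| 20% vs 50% | 0.120 SD | 0.140 SD | 0 |
| 10% vs 50% | 0.161 SD | 0.202 SD | 0 |

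For example, at 20% vs 30% the non-attender means are −0.087 and −0.126, which differ by 0.040 before rounding. At 20% vs 50%, the pair is 0.042 and 0.045 with b = 0.5, r = 0.3, and 0.152 and 0.188 with b = 1.5, r = 0.5.

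**5. Scale.** The standard error of the unstratified two-arm difference is √(2/22) = 0.30 SD. At 20% attendance in both arms, the attender stratum holds 22 × 0.2 = 4.4 per arm, with standard error √(2/4.4) = 0.67 SD.

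At 20% vs 30%, the non-attender strata hold 17.6 and 15.4, with standard error √(1/17.6 + 1/15.4) = 0.349. The attender strata hold 4.4 and 6.6, with standard error √(1/4.4 + 1/6.6) = 0.615. The two-sided type I error is Φ(−1.96 + bias/SE) + Φ(−1.96 − bias/SE). This gives about 5.2% in non-attenders and 5.1% in attenders, against a nominal 5%. Even with the larger bias of 0.052 and the full-sample standard error of 0.30, it is about 5.3%.

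**6. Loss of a real effect.** A separate simulation (2,000,000 participants per scenario, outcome in residual SD units) compared the plain arm difference with one adjusted for attendance. The direct training effect was 0.3 and a course added 0.5.

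- 30% vs 30%: 0.30 without and with adjustment.
- 30% vs 50%, no shared cause: 0.40 unadjusted, 0.30 adjusted.
- 30% vs 50%, motivation adding 0.5 or 1.0 per SD: 0.40 unadjusted, 0.22 or 0.14 adjusted.
- 20% vs 50%, motivation adding 1.0: 0.45 unadjusted, 0.05 adjusted.

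The adjusted estimate can therefore lose much of a real effect when attendance differs widely between arms. The unadjusted estimate keeps the total effect in every case.

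**The case for a change.** The best argument for a change is that the Limitations reasoning is wrong for one of its three factors, whatever the attendance rates turn out to be. Nothing in the text excludes conditioning on that factor: intention to treat settles who is analysed in which arm and does not forbid stratifying on a later event, and analyst blinding does not remove the bias. In the scenarios with unequal attendance, both strata err in the same direction, against the arm with higher attendance, so pooling strata would not cancel the error. One sentence of text would close the matter at almost no cost.

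The methodological part stands. Balance of post-baseline attendance is an assumption, and stratifying on it is unsafe if allocation affects it. The protocol does word it as an expectation, and the expectation is correct if training does not alter course uptake. It is also reasonable for machine access and supervision if these are fixed workplace features.

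The claim that the main analysis is unnamed does not stand. Table 1 names it, and replacing it with a stratified result would be a visible departure from the plan. Asking for machine and supervision items before randomisation does not stand either: the codebook is not available, and the content of the pre-study participant information in Table 2 cannot be seen, so these items may already be there.

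**Conclusion.** No change is needed. Followed as written, the plan gives an unstratified intention-to-treat comparison of the scan count, which is valid whether or not training changes course attendance. What is missing is a label on an optional extra analysis of a secondary outcome. Analysts would ordinarily fill that gap sensibly, by reporting attendance by arm and treating any breakdown by it as exploratory. Strata of about four attenders per arm would discourage leaning on such a breakdown anyway.

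Harm would need several things together: attendance is collected, it is used as a stratum, training arm changes it, and the stratified result displaces the Table 1 analysis. Under the assumed model with no true effect, the false difference is 0 at equal attendance and 0.04 to 0.05 SD at 20% vs 30%. It reaches 0.16 to 0.20 SD only at 10% vs 50%, which is still below the 0.30 SD standard error. Wide gaps are more plausible against untrained controls than between the two trained arms that the Outcomes section compares.

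These sizes rest on assumed attendance rates and motivation effects, since the documents supply neither. The conclusion itself rests on Table 1 being followed.

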Number of examination performed from baseline among the three groups to follow up (4 months)	Training on simulator gives the trainee a better starting point for doing examinations in the clinical daily work	Participant reported number of examinations performed	Gaussian distribution expected, continuous interval data	Parametric analysis, and ANOVA with Bonferroni correction for multiplicity

Table 2. Timeline of measurements

	Pre study (registration and theoretic session)	Baseline (course day)	4 months
Participant information	X		
Theoretical Test	X		
LUS-OSAUS		XX	
Follow-up questionnaire			X
